2.1.3 Efficacy endpoints

2.1.3.1 Primary efficacy endpoint(s)

The primary efficacy endpoint for the Phase 2 part of the study is RR.

For patients with NSCLC, the RR is defined as the proportion of patients achieving complete response (CR) or partial response (PR) as best overall response (BOR), assessed by the investigator per RECIST 1.1 criteria, relative to the total number of patients in the analysis population. The confirmation of complete or partial response is required to determine BOR. BOR will be derived per RECIST 1.1 criteria using disease assessments performed from the first dose of treatment through the study excluding any assessments performed after the cutoff date or following the initiation of a further anticancer treatment. Clinical deterioration will not be considered as progression in the primary analysis of RR.

For patients with mCRPC, response will be defined by radiographic objective response (achieving CR or PR as BOR for soft tissue) assessed and confirmed by the Investigators and/or a PSA decline of $\geq 50\%$ from baseline that is subsequently confirmed per PCWG3 criteria (protocol Appendix A). The PSA decline must be confirmed to be sustained by a second PSA value obtained 4 or more weeks later. BOR for soft tissue will be Non-CR/Non-PD for patients with no baseline target and non-target lesions identified at baseline and no new lesions reported in post-baseline tumor assessments.

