2.1.3.2 Secondary efficacy endpoint(s)

The secondary efficacy endpoints are:

- Tumor burden change: Tumor burden change is defined as the best percent-change from baseline in a sum of the diameters (longest for non-nodal lesion, short axis for nodal lesions) for all target lesions

Area under the curve (AUC) of percent-change from baseline in tumor burden is defined as the area under the percent-change from baseline versus time curve calculated using the trapezoidal method from the date of the first post-baseline assessment to the date of the last assessment

The time-adjusted AUC of percent-change from baseline in tumor burden is defined as AUC of percent-change from baseline in tumor burden divided by the duration of the assessment

- Duration of response: Duration of response is defined as the time from the date of first response (PR or CR in radiographic objective response, or PSA decline $\geq 50\%$ for patients with mCRPC) that is subsequently confirmed to the date of first disease progression or death, whichever occurs first. Disease progression includes radiographic disease progression or unequivocal clinical progression. The RECIST 1.1 criteria will be followed for assessment of radiographic disease progression in patients with NSCLC and the PCWG3 criteria will be followed in patients with mCRPC. For patients with mCRPC, radiographic progression includes progression by PCWG3 modified RECIST 1.1 for soft tissue and/or PCWG3 defined progression by bone scan. In the absence of disease progression or death before the analysis cut-off date or the date of initiation of a further anticancer treatment, the DOR will be censored at the date of the last valid response assessment not showing disease progression performed prior to initiation of a further anticancer treatment and the analysis cut-off date, whichever is earlier. DOR will not be calculated for patients who do not achieve a response

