- Progression-free survival: For mCRPC patients, PFS is defined as the time from first study treatment administration to the date of first documented disease progression or the date of death from any cause, whichever occurs first. Disease progression includes radiographic disease progression (per PCWG3 criteria) or unequivocal clinical progression. For NSCLC patients, PFS is defined as the time from first study treatment administration to the date of first documented radiographic progression (per RECIST 1.1) or the date of death from any cause, whichever occurs first

For patients who did not experience documented disease/radiographic progression or death before the analysis cut-off date or the date of initiation of new anticancer treatment, PFS will be censored at the date of the last valid disease/radiographic assessment not showing disease progression performed prior to initiation of a further anticancer treatment or the analysis cut-off date, whichever comes first. In addition, patient without PFS event (death or documented disease/radiographic progression) and without any valid post-baseline disease assessments will be censored at the day of first treatment (Day 1)

- Disease control rate (DCR): DCR is defined as the proportion of patients with confirmed complete response (CR) or partial response (PR) or stable disease (SD), as assessed by Investigator (per PCWG3 criteria for mCRPC patients and per RECIST 1.1 criteria for NSCLC patients) relative to the total number of patients in the analysis population

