2.1.3.3 Exploratory efficacy endpoint(s)

For patients with mCRPC and patients with NSCLC, the following endpoints will be summarized:

- Overall survival (OS): defined as the time from first study treatment administration to death for any cause. Patients without death prior to the analysis cut-off date will be censored at the last date the patient was known to be alive or the cut-off date, whichever comes first
- Time to response: defined as the time from first study treatment administration to the first response (PR or CR in radiographic objective response, or PSA decline $\geq 50\%$ for patients with mCRPC) that is subsequently confirmed (RECIST 1.1 for patient with NSCLC and PCWG3 criteria for patients with mCRPC)
- PFS by modified response evaluation criteria in solid tumors for immune based therapies (iRECIST) (3): is defined as the time from first study treatment administration to the date of first documented disease progression that is subsequently confirmed or the date of death from any cause, whichever occurs first. The same censoring rule as PFS will be used

In addition, the following endpoints will be summarized for patients with mCRPC:

- Disease control rate (DCR) ≥ 6 months: DCR ≥ 6 months includes patients with BOR of CR or PR of any duration or SD of ≥ 6 months duration. Duration of SD is defined as the time from the date of first treatment to the date of first disease progression or death due to any cause, whichever occurs first. Disease progression includes radiographic disease progression (per PCWG3 criteria) or unequivocal clinical progression. In the absence of disease progression or death before the analysis cut-off date or the date of initiation of a further anticancer treatment, the duration of SD will be censored at the date of the last valid disease assessment not showing disease progression performed prior to initiation of a further anticancer treatment and the analysis cut-off date, whichever is earlier

DCR ≥ 6 months rate is defined as the proportion of patients with DCR ≥ 6 months relative to the total number of patients in the analysis population

Similarly, DCR ≥ 6 months rate requiring PD confirmation will also be summarized

- Radiographic PFS (rPFS): For mCRPC patients, rPFS is defined as the time from first study treatment administration to the date of first documented radiographic progression or the date of death from any cause, whichever occurs first. The same censoring rule as PFS will be used

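### In mCRPC, disease control of at least 6 months, as written, leaves out durable non-progressors whose best response is Non-CR/Non-PD, and plain DCR does not say how to treat them

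*SAP*

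**What the plan says.** **Plain DCR.** SAP 2.1.3.2 says that "DCR is defined as the proportion of patients with confirmed complete response (CR) or partial response (PR) or stable disease (SD". The judgement is made at the site: "as assessed by Investigator (per PCWG3 criteria for mCRPC patients and per RECIST 1.1 criteria for NSCLC patients". The denominator takes everyone: "relative to the total number of patients in the analysis population". Protocol 9.6.2 names the same three categories.

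**DCR of at least 6 months.** SAP 2.1.3.3 defines this for mCRPC only. The numerator "includes patients with BOR of CR or PR of any duration or SD of" a minimum length, set at 6 months. The clock is then fixed: "Duration of SD is defined as the time from the date of first treatment to the date of first disease progression". Death also ends it. Progression there is radiographic per PCWG3 or unequivocal clinical progression. A version requiring confirmed PD is also planned.

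**BOR in mCRPC.** SAP 2.1.3.1 says that "BOR for soft tissue will be Non-CR/Non-PD for patients with no baseline target and non-target lesions identified at baseline". It attaches a condition on the later scans: "no new lesions reported in post-baseline tumor assessments". Protocol Appendix B, Table 14, gives non-target-only disease four possible outcomes: CR, Non-CR/non-PD, inevaluable or PD. SD is not among them. Table 12 defines SD through the sum of target-lesion diameters.

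**Who can enrol.** Protocol 7.2 (I 06) accepts a bone lesion on bone scan as proof of metastatic disease. Protocol 12.2 does not require a measurable lesion in mCRPC. Protocol 12.3.2 and Appendix A (Table 9) keep bone lesions out of RECIST and follow them by bone scan.

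**The concern.** The design admits mCRPC patients who have no soft-tissue target lesions. The SAP foresees the bone-only group and gives it its own label, but neither disease-control definition mentions that label. These patients stay in the denominator, and nothing says whether they can enter the numerator.

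The result can also be inconsistent across endpoints. A bone-only patient with a confirmed PSA decline of at least 50% is a responder for the primary endpoint. Neither disease-control definition lists PSA response, so the same patient could be reported as a responder and as not controlled.

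At stake are a named secondary endpoint, an exploratory endpoint, and the biomarker summaries. SAP 2.4.8 gives DCR of at least 6 months as its example of a clinical grouping in mCRPC. Patients with durable non-progression could land in the comparison group.

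**Working it through.** The plan states no DCR figure, so there is none to reproduce. The check is a reading of the definitions, followed by an illustration of scale.

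**Step 1: is there a mapping?** Non-CR/Non-PD, SD, BOR and DCR were traced through both documents.
- SAP 2.5.2 (data handling for secondary efficacy variables) reads as not applicable.
- SAP 2.4.5.1 only says that BOR is summarized descriptively.
- SAP 2.4.5.2 lists DCR of at least 6 months without a derivation and has no line for plain DCR. Protocol 13.4.4.2 supplies that line, but only as descriptive statistics.
- Protocol Appendix A gives no SD definition for patients without target lesions.

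No section maps Non-CR/Non-PD into or out of disease control.

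**Step 2: DCR of at least 6 months.** The definition is written in terms of BOR, and the only mCRPC BOR defined is the soft-tissue one. A patient whose BOR is Non-CR/Non-PD has neither CR, PR nor SD. The 6-month clock times SD, but it does not say who has SD. Applied as written, the patient is in the denominator and not in the numerator, however long he stays progression-free.

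**Step 3: plain DCR.** The text does not use the term BOR and refers to investigator assessment per PCWG3. If the soft-tissue BOR is used, two errors arise:
- *Downward (d):* progression-free Non-CR/Non-PD patients are left out.
- *Upward (u):* a patient with soft-tissue SD and bone-scan progression at the same assessment is counted as controlled, although progression in mCRPC includes "progression by PCWG3 modified RECIST 1.1 for soft tissue and/or PCWG3 defined progression by bone scan".

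Reported DCR = true DCR − d + u. Neither d nor u can be obtained from the documents, so the sign of the net error is open.

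**Step 4: illustration for DCR of at least 6 months.** Let f be the share of patients with no soft-tissue target lesions, and c the true rate of control for at least 6 months, taken as equal in all patients. Both are assumed. If none of the f group reaches CR, the reported rate is c(1 − f):

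| c | f = 10% | f = 20% | f = 30% |
|---|---|---|---|
| 30% | 27% | 24% | 21% |
| 50% | 45% | 40% | 35% |
| 70% | 63% | 56% | 49% |

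Of 49 patients, these values of f are about 5, 10 and 15. At f = 60%, c = 30% would read 0.30 × 0.40 = 12%. Inclusion criterion I 03 asks for biopsy-amenable disease or archival tissue, which may favour a low f but does not fix it.

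Non-target-only patients can still count through CR. If they make up half of f and 20% of their controlled patients reach CR (both assumed), the rate is c(1 − 0.5f − 0.5f × 0.8) = c(1 − 0.9f). At c = 50% that gives 45.5%, 41.0% and 36.5%.

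**Step 5: biomarker split, same assumptions, N = 49, c = 30%, no CR.** Durably controlled patients: 49 × 0.30 = 14.7. Misplaced: 14.7f = 1.5, 2.9 or 4.4. Size of the comparison group: 49 − 14.7(1 − f) = 35.8, 37.2 or 38.7. Misplaced share of that group: 4%, 8% or 11%.

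**The case against.** The strongest reply is that the intent is clear enough. The Non-CR/Non-PD sentence sits under the primary endpoint and is limited to soft tissue. Plain DCR relies on the investigator's PCWG3 assessment. The SD clock stops at PCWG3 or clinical progression, an event that can be determined in any mCRPC patient. A programmer could reasonably treat non-progression as SD. This stands as evidence of likely intent, and it is why plain DCR is called ambiguous here and not wrong. It does not supply the rule, and two competent programmers could report different rates from the same data.

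It also stands that PFS, radiographic PFS and PFS at 6 months already describe these patients, that the biomarker grouping is only an example, and that every input to the illustration is assumed. A strict CR/PR/SD count would be a legitimate choice if it were stated.

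A reader might infer three stronger points, and the documents support none of them:
- *Plain DCR is biased downward.* The upward error in Step 3 may offset or exceed the downward one.
- *Every progression-free patient without target lesions is counted as not controlled.* Non-target-only patients who reach CR under Table 14 do count.
- *The primary result is affected.* Response rate counts only CR, PR or PSA response, so the treatment of Non-CR/Non-PD does not change it.

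**Conclusion.** The gap is real and worth closing before database lock, so that the rule is not chosen after results are seen. For DCR of at least 6 months, the text applied literally omits patients whose BOR is Non-CR/Non-PD, and that omission can only lower the rate. For plain DCR the rule is unspecified and the net direction is not established.

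The size is unknown, because neither document gives the share of mCRPC patients without target lesions. The figures above show scale only, under an assumed share and an equal control rate in all patients. The effect is confined to descriptive secondary and exploratory summaries. Response rate, the Simon boundaries, PFS and radiographic PFS do not depend on it.

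**What to change.** State one rule for all mCRPC patients in SAP 2.1.3.2 and 2.1.3.3:

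- Disease control is CR or PR (confirmed, as now), or SD or Non-CR/Non-PD, at one or more evaluable post-baseline disease assessments made before first progression. Progression is PCWG3 soft-tissue and/or bone-scan progression, or unequivocal clinical progression, and applies to every patient whatever the lesion type.
- Later progression does not remove a patient from DCR. Non-CR/Non-PD at week 9 followed by progression at week 18 counts, just as SD at week 9 would.
- For DCR of at least 6 months, SD and Non-CR/Non-PD must both reach 6 months on the existing clock, from first treatment to first progression or death, with the existing censoring.
- Any biomarker grouping by DCR of at least 6 months (SAP 2.4.8) uses the same rule.

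Optionally, show the strict CR/PR/SD count over the same denominator beside it.

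The cost is one derivation rule in two SAP sections, on data already collected, and at most one extra table row. The downside is that the numerator then includes patients whose control rests on absence of progression and not on measured target lesions. The strict count would show how many.

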2.1.3.3 Exploratory efficacy endpoint(s)

For patients with mCRPC and patients with NSCLC, the following endpoints will be summarized:

- Overall survival (OS): defined as the time from first study treatment administration to death for any cause. Patients without death prior to the analysis cut-off date will be censored at the last date the patient was known to be alive or the cut-off date, whichever comes first
- Time to response: defined as the time from first study treatment administration to the first response (PR or CR in radiographic objective response, or PSA decline $\geq 50\%$ for patients with mCRPC) that is subsequently confirmed (RECIST 1.1 for patient with NSCLC and PCWG3 criteria for patients with mCRPC)
- PFS by modified response evaluation criteria in solid tumors for immune based therapies (iRECIST) (3): is defined as the time from first study treatment administration to the date of first documented disease progression that is subsequently confirmed or the date of death from any cause, whichever occurs first. The same censoring rule as PFS will be used

In addition, the following endpoints will be summarized for patients with mCRPC:

- Disease control rate (DCR) ≥ 6 months: DCR ≥ 6 months includes patients with BOR of CR or PR of any duration or SD of ≥ 6 months duration. Duration of SD is defined as the time from the date of first treatment to the date of first disease progression or death due to any cause, whichever occurs first. Disease progression includes radiographic disease progression (per PCWG3 criteria) or unequivocal clinical progression. In the absence of disease progression or death before the analysis cut-off date or the date of initiation of a further anticancer treatment, the duration of SD will be censored at the date of the last valid disease assessment not showing disease progression performed prior to initiation of a further anticancer treatment and the analysis cut-off date, whichever is earlier

DCR ≥ 6 months rate is defined as the proportion of patients with DCR ≥ 6 months relative to the total number of patients in the analysis population

Similarly, DCR ≥ 6 months rate requiring PD confirmation will also be summarized

- Radiographic PFS (rPFS): For mCRPC patients, rPFS is defined as the time from first study treatment administration to the date of first documented radiographic progression or the date of death from any cause, whichever occurs first. The same censoring rule as PFS will be used
- rPFS by iRECIST: For mCRPC patients, rPFS is defined as the time from first study treatment administration to the date of first documented radiographic progression that is subsequently confirmed or the date of death from any cause, whichever occurs first. The same censoring rule as PFS will be used
- PSA response rate: defined as a PSA decline of $\geq 50\%$ from baseline that is subsequently confirmed
- Radiographic RR: defined as radiographic objective response assessed and confirmed by investigator

- Duration of PSA response: defined as the time from the date of the PSA first decline of $\geq 50\%$ from baseline that is subsequently confirmed to the date of first confirmed PSA progression or death, whichever occurs first. PSA progression for patients who have achieved a $\geq 50\%$ decrease from baseline is defined as at least a 25% increase and an absolute increase of ≥ 2 ng/mL above the nadir (the lowest PSA value on study). The same censoring rules as for DOR will be used
- Duration of radiographic response: defined as the time from the date of the first radiographic response (PR or CR) that is subsequently confirmed to the date of first radiographic progression or death, whichever occurs first. The same censoring rules as for DOR will be used
- Time to PSA response: defined as the time from first study treatment administration to the first PSA response that is subsequently confirmed
- Time to radiographic response: defined as the time from first study treatment administration to the first radiograph response that is subsequently confirmed
- Time to PSA progression: defined as the time from first study treatment administration to the date of first confirmed PSA progression. For patients who have achieved a $\geq 50\%$ decrease from baseline, PSA progression is defined as at least a 25% increase and an absolute increase of ≥ 2 ng/mL above the nadir (the lowest PSA value on study). For patients without a PSA decrease of this magnitude or no decrease at all, PSA progression is defined as at least a 25% increase and an absolute increase of ≥ 2 ng/mL above the baseline. Death from prostate cancer or any other cause without prior evidence of PSA progression will not count as an event. If no event exists, then time to PSA progression will be censored at the last scheduled PSA assessment on study or date of death, whichever occurs first

For patients with NSCLC, the following endpoint will also be summarized:

- ORR by iRECIST (NSCLC patients): defined as the proportion of patients achieving complete response (CR) or partial response (PR) as best overall response (BOR) as assessed by the investigator per iRECIST criteria relative to the total number of patients in the analysis population

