#### For mCRPC patients (I05 to I11):

- I 05. Histologically confirmed adenocarcinoma of the prostate (excluding neuroendocrine differentiation and/or small cell features).
- I 06. Metastatic disease documented by bone lesion on bone scan, or by measurable soft tissue disease by computed tomography (CT) or magnetic resonance imaging (MRI). Patients whose disease spread is limited to regional pelvic lymph nodes are not eligible.
- I 07. Surgically or medically castrated, with testosterone levels of <50 ng/dL (<2.0 nM). Patients who have not had a bilateral orchiectomy must have started androgen deprivation therapy with gonadotropin-releasing hormone (GnRH) analogue ≥4 weeks prior to initiation of IMP and continue such therapy throughout the study.
- I 08. At least 1 but no more than 2 previous androgen receptor-targeted agents (abiraterone and enzalutamide).

- I 09. Received up to 2 previous taxane-based chemotherapy regimens as per local standard of care (for example, docetaxel followed by cabazitaxel), unless per investigator's judgement a chemotherapy regimen is not appropriate for the specific patient. If the same taxane-based chemotherapy is used more than once, this will be considered as 1 regimen.
- I 10. No previous radium 223.
- I 11. Documentation of PD as assessed by the Investigator with at least 1 of the following within 6 months prior to first dose of IMP per Prostate Cancer Clinical Trials Working Group 3 (PCWG3) criteria (Appendix A) during or following the direct prior line of therapy.
  - Prostate-specific antigen progression defined by a minimum of 2 rising PSA levels with an interval of ≥1 week between each determination. The PSA value at the Screening visit should be ≥1 μg/L (1 ng/mL) if confirmed rise is the only indication of progression. Patients on systemic glucocorticoids for control of symptoms must have documented PSA progression while on systemic glucocorticoids before initiation of IMP.

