#### Disease assessment

- Tumor imaging: CT or MRI scan of the chest, abdomen, pelvis and any other locations with suspicion or evidence of disease involvement (the same method of assessment should be used throughout the study). The initial tumor imaging will be performed within 28 days screening period (as close as possible to initiation of IMP). Scans performed as part of routine clinical management are acceptable for use as the screening scan if they are of diagnostic quality and performed within 28 days before IMP initiation.
  - mCRPC: Measureable lesion per RECIST 1.1 per local reading is not mandatory.
  - NSCLC: Patients with NSCLC must have at least 1 radiographically measurable lesion per RECIST 1.1 per local reading.
- Prostate-specific antigen assessment for patients with mCRPC (local laboratory).
- Bone scan for patients with mCRPC: The initial scan will be performed within 28 days screening period (as close as possible to initiation of IMP). Scans performed as part of routine clinical management are acceptable for use as the screening scan if they are of diagnostic quality and performed within 6 weeks before IMP initiation. In case of doubtful lesions on bone scan, bone-centered X-ray or MRI scan should be performed to confirm the nature of those lesions (metastatic or not).

All patients who signed the study informed consent form will be assigned a patient number. Each patient will receive an incremental identification number corresponding to his/her order of enrollment in the study. Those patients, who meet all the inclusion criteria and none of the exclusion criteria, will be eligible for registration in the study. A written confirmation of each eligible patient identification and treatment dose level will be forwarded to the Investigator.

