2.3.7 Response evaluable population

The response evaluable population will include all patients in the all-treated population who fulfilled all inclusion and exclusion criteria with an evaluable baseline assessment and at least one evaluable post-baseline disease assessment during the treatment period.

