2.4.5 Analyses of efficacy endpoints

All efficacy analysis will be performed using the all-treated population. In addition, efficacy analysis will be performed using the response evaluable population.

For each cohort, the analysis cut-off date for the primary analysis of RR will be 6 months after the last patient's first treatment in the cohort. The analysis cut-off date for secondary efficacy endpoints including DoR and PFS will be 12 months after the last patient's first treatment in the cohort. The primary analysis of RR will be updated.

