2.4.5.2 Analyses of secondary efficacy endpoints

The secondary efficacy endpoints are:

- Tumor burden change: the best percent-change from baseline in tumor burden will be summarized and presented graphically for patients with measurable disease at baseline. In addition, a summary of the AUC and the time-adjusted AUC of percent-change from baseline in tumor burden will also be provided as an exploratory analysis
- DoR: Kaplan-Meier estimates such as median and Kaplan-Meier curves will be provided for patients who achieved a response (PR or CR, or PSA response for mCRPC patients)
- PFS: the PFS will be analyzed using the Kaplan-Meier method. The Kaplan-Meier estimates of the 25th, 50th and 75th percentiles and the 95% confidence intervals of median will also be computed. The Kaplan-Meier curves will be plotted. In addition, PFS at 6 months will also be provided

DCR \geq 6 months, PSA response rate, radiographic RR for mCRPC patients and ORR by iRECIST for NSCLC patients will be summarized with descriptive statistics. OS, time to response, and PFS by iRECIST will be analyzed using the Kaplan-Meier method. In addition, for mCRPC patients, rPFS, rPFS by iRECIST, duration of PSA response, duration of radiographic response, time to PSA response, time to radiographic response, and time to PSA progression will be also be analyzed using the Kaplan-Meier method.

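### In the mCRPC cohorts, radiographic response rate counts patients with no soft-tissue lesion, who cannot respond, in its denominator; add a rate among patients who can

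*SAP*

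**What the plan says.** SAP 2.1.3.3 lists among the exploratory mCRPC endpoints "Radiographic RR: defined as radiographic objective response assessed and confirmed by investigator". That line names no denominator. SAP 2.4.5 supplies two: "All efficacy analysis will be performed using the all-treated population", followed by "In addition, efficacy analysis will be performed using the response evaluable population". SAP 2.3.7 limits the second population to eligible treated patients "with an evaluable baseline assessment and at least one evaluable post-baseline disease assessment during the treatment period".

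On who may enter, inclusion criterion I 06 (Protocol 7.2) accepts "Metastatic disease documented by bone lesion on bone scan, or by measurable soft tissue disease", and Protocol 12.2 adds "mCRPC: Measureable lesion per RECIST 1.1 per local reading is not mandatory".

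On what counts as a response, SAP 2.1.3.1 ties radiographic response in mCRPC to CR or PR as best overall response in soft tissue. It assigns Non-CR/Non-PD to patients who have neither target nor non-target lesions at baseline and no new lesions later. Table 9 in Protocol Appendix A assesses bone lesions by bone scan only and gives the response criteria for that scan as not applicable.

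SAP 2.4.5.2 summarises radiographic RR descriptively and names no subset. In the same section, best percent-change in tumour burden is summarised and "presented graphically for patients with measurable disease at baseline".

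**The concern.** A response rate is easiest to read when everyone in the denominator could have responded. Here some mCRPC patients are fixed as non-responders from the day they enter, whatever the drug does. The reported rate then mixes activity in soft tissue with the proportion of enrolled patients who have soft-tissue disease.

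The plan restricts tumour burden change to patients with measurable disease but applies no such restriction to radiographic RR. A reader also could not reliably undo the mixing. The mCRPC study-entry characteristics in SAP 2.1.1 are disease extent, criteria for progression and baseline PSA. Neither measurable disease nor the presence of a soft-tissue lesion is listed.

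What is at stake is the interpretation of one exploratory figure, not a trial decision.

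**Working it through.** **The plan's own figures.** The documents state no figure for radiographic RR. The only mCRPC response design is for the composite primary RR (Protocol 13.1, Table 8): 23 then 49 patients, at least 3 then at least 9 responses, H0 10%, H1 26%. The exact probability of success is the sum over x from 3 to 23 of P(X1 = x; n = 23) × P(X2 ≥ 9 − x; n = 26).

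- At 10% this is 0.0479, within the 5% one-sided level.
- At 26% it is 0.9015, matching the stated 90% power.

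The design reproduces, and nothing below alters it.

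**Do patients without soft-tissue lesions stay in the denominator?**

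1. They are eligible: I 06 accepts bone lesions alone.
2. They cannot respond radiographically: response is CR or PR in soft tissue, and the bone scan has no response category (Table 9).
3. All-treated population: one dose is enough for inclusion, so they are in.
4. Response evaluable population: the definition does not require soft-tissue or measurable disease. It does not say which kind of assessment must be evaluable, so a bone scan or PSA could satisfy it. They can be in.
5. Percentage rule in SAP 2.5.3: denominators count non-missing observations. These patients have an assigned best overall response, so the rule does not remove them.

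**Size.** Let N be treated mCRPC patients, S those with any target or non-target soft-tissue lesion at baseline, and x the radiographic responders. All responders come from S, so

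x/N = (S/N) × (x/S).

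The share S/N is not in the documents. The values below are assumptions. The last column illustrates x = 6 and N = 49 with 90% Clopper-Pearson intervals, the method that SAP 2.4.5.1 specifies for the primary RR. S is rounded from 49 × share (39.2, 29.4, 19.6).

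| Assumed share S/N | A 20% rate in S is reported as | 6 responders, denominator S |
|---|---|---|
| 80% | 0.20 × 0.8 = 16% | 6/39 = 15.4% (6.9 to 28.1) |
| 60% | 0.20 × 0.6 = 12% | 6/29 = 20.7% (9.4 to 36.8) |
| 40% | 0.20 × 0.4 = 8% | 6/20 = 30.0% (14.0 to 50.8) |

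The all-treated line for the same six responders is 6/49 = 12.2% (5.5 to 22.7) in every row.

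**Which patients cannot respond?** The identity holds for patients with any soft-tissue lesion, not only for those with measurable disease. In Protocol Appendix B, Table 14, a patient with non-target disease only can reach CR. A denominator of measurable patients therefore needs its own numerator, taken from those same patients.

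**The case against.** The strongest reply is that all-treated is the pre-specified primary efficacy population in both documents and is conservative for a rate. Radiographic RR is exploratory and descriptive, and nothing depends on it. Stage 2 and the test of H0 use the composite RR, in which a bone-only patient can respond by PSA, and PSA response is also reported separately. All of this stands, and it is why the point is minor.

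A second reply is that planned output already shows part of the case mix: the best overall response table, the tumour burden summary in patients with measurable disease, and the progression criteria at entry. This stands only in part. Non-CR/Non-PD also covers persisting non-target disease, and the tumour burden count omits patients with no post-baseline measurement.

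Three stronger readings are tempting but not supported:

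- **That every patient without measurable disease is a certain non-responder.** Table 14 allows CR with non-target disease only.
- **That the plan offers no other denominator.** The response evaluable analysis is planned. The narrower point is that its definition does not remove these patients.
- **That the endpoint fails as a comparison between cohorts or with other trials.** The study is declared non-comparative, and Protocol 13.1 says that the randomisation is not meant for comparing Cohorts A-1 and A-2. Patients randomised to A-2 and to Stage 2 of A-1 should also have a similar bone-only share in expectation. For other trials, the documents do not establish which denominators were used.

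**Conclusion.** The point holds as a reporting gap. Under both planned populations, mCRPC patients with no soft-tissue lesion at baseline can count as certain radiographic non-responders. The reported rate equals the rate among patients with soft-tissue disease multiplied by their share of the population.

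The size depends entirely on that share, which the documents do not give. At assumed shares of 80%, 60% and 40%, a 20% rate is reported as 16%, 12% and 8%. If nearly all patients have a soft-tissue lesion, the effect is negligible.

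The conclusion also rests on reading bone lesions as assessed by bone scan only, as Table 9 and Protocol 12.3.2 say for mCRPC. The general text of Appendix B would let some lytic lesions with a soft-tissue component count as measurable.

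A reader might infer that the primary result or the stage decisions are biased. They are not affected: the composite RR, its thresholds, the sample sizes and the error rates are unchanged.

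**What to change.** In SAP 2.1.3.3 and 2.4.5.2, keep the all-treated radiographic RR and add, for each mCRPC cohort, the same rate with a 90% Clopper-Pearson interval in:

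- all treated patients with any target or non-target soft-tissue lesion at baseline;
- all treated patients with measurable disease at baseline.

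Take numerator and denominator from the same patients in each row, count patients without a post-baseline assessment as non-responders, and print each denominator. Fixing the definitions before results are seen prevents a later choice of denominator.

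The cost is one or two table rows from baseline lesion data already collected, and wider intervals because the denominators are smaller. In the illustration with a 60% share, the interval runs from 9.4% to 36.8%, against 5.5% to 22.7% for all treated patients.
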